3.2 Study Design and Procedures

This is a randomized controlled trial (RCT) that employs an experimental mixed design where group (traditional Yo-Yo, ball-dribbled Yo-Yo, SSGs) serves as a between-subject factor, while time (pre, post) functions as a within-subject factor. The participants will be randomly assigned to one of the groups: the traditional Yo-Yo group, the ball-dribbled group, SSGs group utilizing computer-based random sorting and grouping, where each participant will receive a number and will then be randomly placed into one of the four groups using Research Randomize ((Karahan, 2012; Shaw et al., 2019) When randomly grouping, the researcher in charge does not participate in the pre- and post-tests.

This research will utilize a non-blinded grouping randomization. The recruited participants who achieve the inclusion criteria will firstly be numbered in sequence then randomly allocated to one of the four groups. Secondly, all participants should experience the baseline testing within 2-weeks before the intervention. The anthropometric parameters, aerobic and anaerobic abilities will be assessed during this stage. The anthropometric indexes and one anaerobic assessment (Wingate Anaerobic Test) will be conducted in kinesiology Laboratory, University of Macau. The aerobic ability and the other anaerobic assessment (Sprint test and Repeated Sprint Ability test) will take place in the playground of a middle school. Then, the intervention will last for four weeks, with 3 training session per week, 12 sessions in total, which will take place in the playground of a middle school. Finally, the post-test stage, all the measurements conducted in the pre-test should be completed within 1-week following the last training session. During the pre- and post-test period, the researchers involved in the test were not informed of the intervention

groups of the subjects. All the procedures are shown in the flow chart as follows (figure 1).

Figure 1 *Study Flowchart*

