1.2 Purpose of the Study

This study aims to investigate the differential effects of three training protocols:

traditional Yo-Yo intermittent training, ball-dribbled Yo-Yo intermittent training, and small-sided games (SSGs) on aerobic capacity, anaerobic and soccer-specific performance in adolescent soccer players following a 4-week intervention.

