1.4 Hypothesis of the Study

H1: The aerobic capacity of adolescent soccer players will improve following a 4-week intervention.

H2: The anaerobic performance of adolescent soccer players will improve following a 4-week intervention.

H3: Aerobic adaptations will be equivalent between traditional Yo-Yo and ball-dribble Yo-Yo groups, with both superior to SSGs.

H4: Anaerobic performance will be equivalent between ball-dribble Yo-Yo and SSGs groups, with both superior to traditional Yo-Yo.

Chapter 2 Literature Review

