3.1 Participants

Participants should be recruited from middle school soccer teams. Participants shall fulfill all the following inclusion criteria to be included in the study: (1) be aged between 13 and 18 years; (2) have received at least one year of formal football training; (3) have no history of major sports-related injuries; (4) be in good general health, without smoking or alcohol consumption habits; and (5) have no known psychological or psychiatric disorders that may affect participation; (6) have not participated in any similar intervention within the past year; (7) attend the training sessions regularly. Participants should be excluded according to the following criteria: 1. are outside the age range of 13–18 years; 2. have less than one year of formal football training experience; 3. have a history of major sports-related injuries; 4. have chronic diseases or unhealthy habits such as smoking or alcohol consumption; 5. have known psychological or psychiatric disorders that may affect participation; 6. have participated in similar training interventions within the past year; 7. fail to attend at least 75% of the 12 training sessions.

The required sample size was calculated using G*Power 3.1 software based on a repeated-measures ANOVA (within-between interaction). The average effect size (f) was set at 0.25 (Cherni et al., 2025; Li et al., 2022), with a significance level of 0.05, and the desired statistical power of 0.80 achieved. The calculations indicated that a minimum of 42 participants are required in total, considering the 20% dropout, at least 50 participants should be recruited at the screening session.

The experimental procedures will be explained to participants and their parents at the screening-baseline. Before data collection, the written informed consent should also be provided. During the study, the participants will all attend regular schools and

football trainings. This research should receive approval from the Ethics Committee of University of Macau.

[figure not shown]

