3.3 Intervention

Participants will receive traditional Yo-Yo training, ball-dribbled Yo-Yo training, SSGs training respectively. The intervention will last for 4-weeks, with 3 training sessions a week. These interventions will perform as regimens at the same time into the whole training. The first 2-weeks training consists of 2 sets 4-minutes exercise and a 4-minutes passive rest. During the last 2-weeks, the rest between exercise will be reduced to 3-minutes. While training, all the participants should

wear a heart rate belt (Verity Sensebi, Polar, Finland) to monitor the training intensity. Heart rate and RPE will be recorded before, during and after the training.

The Yo-Yo Intermittent Recovery 1 protocol will be implemented as a training tool. Participants should perform 4-minutes repeated 20-meter shuttle runs between two parallel lines, with running pace controlled by standardized audio cues, followed by a 10-second passive rest. The speed will initially start from 10 km/h, increasing by 0.5 km/h every stage. The termination rules will be cancelled, and participants should try to maintain maximum effort regardless of the cues.

The Ball-dribbled Yo-Yo Intermittent training requires participants performing repeated shuttle runs with a soccer ball, simulating dribbling with maximum effort in game. Each shuttle lasts 15 seconds, followed by 15 seconds of passive rest. The required shuttle distance per bout is calculated based on 110% of participant's baseline Yo-Yo IR1 terminal speed. Individualized bout distances will calculate as:

$$D = (V_t \times 110\% / 3.6) \times 15$$
 Where: D = Required shuttle distance per bout (meters), V_t = Terminal speed (km/h) from pre-test Yo-Yo IR1 (Appendix 1) and 3.6 = km/h to m/s conversion. The turning point of the shuttle run will be marked with cone for participant, where participants need to turn 180° with ball dribbled. To ensure continuity of play, two coaches will be positioned near the sidelines to provide replacement balls when necessary.

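### Section 3.2 allocates players to four groups when the plan defines three, and with every arm trained the time effect behind H1 and H2 cannot be credited to the programmes

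*Combined protocol and SAP*

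**What the plan says.** **Number of groups.** Section 3.2 describes the allocation twice. In the first paragraph each numbered player "will then be randomly placed into one of the four groups using Research Randomize". In the second, eligible players are numbered in sequence and "then randomly allocated to one of the four groups". The first paragraph also says that "group (traditional Yo-Yo, ball-dribbled Yo-Yo, SSGs) serves as a between-subject factor", and the sentence with the first *four* begins by naming those three groups as the destinations.

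Elsewhere the count is three. Section 1.2: "This study aims to investigate the differential effects of three training protocols". Section 3.3: "Participants will receive traditional Yo-Yo training, ball-dribbled Yo-Yo training, SSGs training respectively". Table 1 has three programme columns. No section names or describes a fourth group, and neither an allocation ratio nor a method of restriction is given.

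**Comparator.** H1 in section 1.4 reads "The aerobic capacity of adolescent soccer players will improve following a 4-week intervention", and H2 says the same of anaerobic performance. Q1 and Q2 in section 1.3 ask how the three programmes *influence* these outcomes. Section 3.1 states that during the study "the participants will all attend regular schools and" football training. Section 3.5 provides a group by time repeated-measures ANOVA. No untrained or usual-training arm is described.

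**The concern.** The number of groups is what the operator enters in the randomisation tool, and the only two sentences that describe the procedure give a number that the rest of the plan contradicts. A list made for four groups would send about a quarter of the players to an arm with no content. That cannot be repaired once players have been allocated.

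The second matter is independent of the first: changing four to three neither creates nor removes a comparator. H1 and H2 predict improvement from pre-test to post-test, so in the planned ANOVA they rest on the time effect. Randomisation does not protect that effect when every arm is trained. Read with Q1 and Q2, a significant time effect would be taken as evidence that the programmes work, although other causes act on all three arms over the same weeks.

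**Working it through.** **Inputs.** From section 3.1: within-between interaction of a repeated-measures ANOVA, f = 0.25, alpha 0.05, power 0.80, minimum total 42, dropout 20%, at least 50 recruited. From section 3.2: two time points (m = 2). Not stated: the number of groups k entered in the calculation, and the correlation rho between the repeated measures. I assume rho = 0.5 and show a range.

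**Formula.** Noncentral F with lambda = f² × N × m / (1 − rho), df1 = (k − 1)(m − 1), df2 = (N − k)(m − 1).

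**Step 1: reproduce the plan's 42.** With k = 3, N = 42, rho = 0.5: lambda = 0.0625 × 42 × 2 / 0.5 = 10.5, df 2 and 39, power 0.803. This is the smallest N that reaches 0.80, so the stated figure is matched exactly.

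**Step 2: try four groups.** With k = 4 and N = 42: lambda is again 10.5, df 3 and 38, power 0.736. Four groups need N = 48 (lambda = 12, df 3 and 44, power 0.803). At rho = 0.5, the plan's figure therefore fits three groups and not four. The required N depends strongly on rho:

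| rho | N, three groups | N, four groups |
|---|---|---|
| 0 | 81 | 92 |
| 0.3 | 60 | 68 |
| 0.5 | 42 | 48 |
| 0.7 | 27 | 32 |
| 0.8 | 21 | 24 |

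**Step 3: literal four-way allocation of 50.** Expected number in the undefined arm: 50 / 4 = 12.5. In the three real arms: 50 × 3/4 = 37.5, and after 20% dropout 37.5 × 0.8 = 30. The like-for-like comparison is three-way allocation of the same 50: 50 × 0.8 = 40 completers.

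| Completers in the three arms | lambda (rho = 0.5) | df | Power |
|---|---|---|---|
| 40 (three-way allocation) | 10.0 | 2, 37 | 0.781 |
| 30 (four-way allocation) | 7.5 | 2, 27 | 0.635 |

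The loss is 0.781 − 0.635 = 0.146, about 15 percentage points. Across other correlations, power at 30 completers is 0.36 (rho 0), 0.49 (rho 0.3), 0.64 (rho 0.5) and 0.86 (rho 0.7).

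**Step 4: what the time effect contains.** No arithmetic applies here; the sections are set side by side.

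- Growth: section 2.1 says that boys gain substantially in strength and aerobic capacity during puberty, and section 2.4 says that the capacities under study develop markedly in adolescence. Eligible ages are 13 to 18.
- Usual training: section 3.1 keeps every player in regular football training.
- Retest: section 3.2 repeats all pre-test measurements within one week after the last session. The traditional Yo-Yo arm also trains on the shuttle format of the aerobic test (sections 3.3 and 3.4.1).

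Each can produce a pre-to-post change without any programme effect, and no arm measures how large that change would be. Growth and usual training act on all arms alike in expectation, so the missing control does not undermine the randomised contrasts between arms.

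**The case against.** **The slip is harmless in practice.** The sentence with the first *four* also names the three destinations, every other section agrees, and staff could not run an arm that has no content. This largely stands. A careful reader would infer three, and a reader who concludes that the allocation rule is unusable goes further than the text allows. The power loss in step 3 is likewise conditional: it occurs only if a quarter of the players really are sent to an undefined arm. What does not stand is leaving the text as it is. The number appears twice, no allocation ratio settles it, and an allocation procedure should not depend on inference.

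**A control arm must have been dropped.** A reader might infer this from the word *four*. The documents do not support it: that word is the only trace, and the sample size fits three groups under the assumed correlation. A drafting slip explains the text equally well. The flowchart (Figure 1) is not available in the text reviewed, so it settles nothing either way.

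**The loss is from 80% to 64%.** This too is tempting, but it compares 42 completers with 30. The 80% belongs to the 42 the plan requires, whereas 50 recruited with 20% dropout leave 40 even under correct allocation. The first two points of that fall come from the recruitment target and have nothing to do with the number of groups.

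**Three active arms are a legitimate design.** They are, for the stated purpose of comparing three programmes. H1 and H2 taken alone are also only temporal, and no section says outright that a time effect will be credited to training. The attribution problem comes from reading them with Q1 and Q2, which ask about influence. The plan gives no figure for growth or retest gain over four weeks, so the size of this bias cannot be stated. That limits what can be said about magnitude; it does not turn an uncontrolled change into an effect of training.

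**Conclusion.** Both parts hold, as two separate corrections. The number of groups in section 3.2 is wrong in both places relative to the rest of the plan. If it were followed literally, 30 rather than 40 completers would remain in the real arms and interaction power would be 0.64 rather than 0.78. Those figures rest on rho = 0.5, an assumption supported only by the fact that it reproduces 42 with three groups.

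H1 and H2, as tested by the time effect, can show that players changed over the four weeks but not that the programmes changed them. This conclusion needs no numerical assumption; it follows from the absence of an untrained or usual-training arm. It does not extend to the between-arm contrasts in H3 and H4, and the documents give no ground for calling the three-arm design itself invalid.

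**What to change.** 1. In section 3.2, change four to three in both sentences and generate the allocation list for the three named arms before the first player is randomised. Check that Figure 1 shows the same three arms. Blocking or a fixed ratio would be a separate choice and is not needed to correct this error.
2. In section 3.1, state the number of groups and the correlation used in the sample-size calculation, so that 42 can be traced.
3. In section 1.4, restate H1 and H2 as descriptive within-arm change over the four weeks, and align Q1 and Q2 with that. In section 3.5, state that the time effect will not be attributed to the programmes and that causal conclusions are confined to the between-arm contrasts in H3 and H4.

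If the investigators did intend a fourth arm, the text would instead have to define it, and the same inputs at rho = 0.5 would require 48 completers, or 48 / 0.8 = 60 recruited.

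The first two changes cost only wording. The third adds no player, visit or test, but it has a real price: H1 and H2 no longer support a claim that the programmes caused the improvement.

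### Players are allocated before effort-dependent baseline tests, and the plan does not say the arm is withheld from them, so baseline performance scores can depend on the arm.

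*Combined protocol and SAP*

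**What the plan says.** Section 3.2 (Study Design and Procedures) puts the steps in order. Eligible players are first numbered and then "randomly allocated to one of the four groups. Secondly, all participants should experience the baseline testing within 2-weeks before the intervention". (The text says four groups although three are defined; that is a separate inconsistency.) The same paragraph opens with "This research will utilize a non-blinded grouping randomization".

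Two safeguards are given, both for staff. When groups are formed, "the researcher in charge does not participate in the pre- and post-tests". At the pre- and post-tests, "the researchers involved in the test were not informed of the intervention" groups. Nothing comparable is stated for players or coaches.

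Section 3.3 (Intervention) ties one arm's training to the baseline result. For ball-dribbled Yo-Yo, "The required shuttle distance per bout is calculated based on 110% of" the player's pre-test Yo-Yo IR1 terminal speed. The other two arms' training is not set from a baseline score.

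Section 3.5 (Statistical Analysis) analyses aerobic and anaerobic performance by a group x time repeated-measures ANOVA on the pre and post values.

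**The concern.** A baseline is protected from the influence of allocation when it is measured before allocation, or while the arm is unknown to those who can affect the score. Here the written order gives the first protection up, and the text does not supply the second for players.

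This matters because the main performance outcomes are volitional. Section 3.4 measures a shuttle run to failure, a 30-second all-out cycle sprint, maximal 10 m and 30 m sprints, and repeated 40 m shuttle sprints. A player who knows his arm may try harder or less hard, and an uninformed tester cannot prevent that. The dribbling arm has a specific incentive: a lower terminal speed means a shorter required distance in all 12 sessions. That incentive exists in one arm only, so it would not cancel between arms.

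With two time points, the group x time test is equivalent to a one-way ANOVA on change scores. A false shift in one arm's baseline therefore becomes a false difference in improvement of the same size, in the comparison that research questions 3 and 4 rest on.

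**Working it through.** **The plan's own figure.** Section 3.1 gives f = 0.25, alpha 0.05, power 0.80 and a minimum of 42 players. For the within-between interaction, lambda = f^2 x N x m / (1 - r). With three groups, m = 2 time points and an assumed r = 0.5 (the plan states no correlation), lambda = 0.0625 x 42 x 2 / 0.5 = 10.5 on (2, 39) degrees of freedom. Power is 0.803, so 42 reproduces. It is used below as 14 per arm. Reordering the steps does not alter it.

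**False-positive rate of the planned test.** Assume no true difference between arms and one arm's baseline shifted by b baseline SDs.

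- Variance of a change score, in SD units: 2(1 - r).
- Sum of squared deviations of the three arm means when one is shifted by b: (2/3)b^2.
- Noncentrality: lambda = 14 x (2/3) x b^2 / [2(1 - r)], referred to F(2, 39).
- Example: b = 0.3, r = 0.5 gives 14 x 0.6667 x 0.09 / 1 = 0.84, and a rejection rate of 11.3% at nominal 5%.

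| Assumed shift b | r = 0.5 | r = 0.8 |
|---|---|---|
| 0 | 5.0% | 5.0% |
| 0.1 SD | 5.7% | 6.7% |
| 0.2 SD | 7.7% | 12.1% |
| 0.3 SD | 11.3% | 22.0% |

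A simulation of 40,000 trials per cell agreed to within about half a percentage point. The sign of the shift does not affect these rates.

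**Other analyses under the same assumptions.** Baseline-adjusted ANCOVA carries a bias of r x b instead of b, with residual variance 1 - r^2. Its noncentrality is 14 x (2/3) x (r b)^2 / (1 - r^2) on (2, 38) degrees of freedom. For shifts of 0.2 and 0.3 SD this gives 5.9% and 7.0% at r = 0.5, and 9.9% and 16.7% at r = 0.8. The bias is smaller but not removed, because the covariate is itself measured after allocation. A comparison of post-test scores alone does not use the baseline, so this source of bias does not enter; the price is lost power when pre and post are well correlated.

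**In test units.** The equation in section 3.4.1 converts 40 m of Yo-Yo IR1 distance to 0.0084 x 40 = 0.336 ml/kg/min. That much is added to the apparent gain for each 40 m not run at baseline.

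**Training distance.** Section 3.3 gives D = (Vt x 1.10 / 3.6) x 15. One 0.5 km/h step lower in Vt shortens D by 0.5 x 1.10 / 3.6 x 15 = 2.29 m. At 15 s work and 15 s rest there are 8 shuttles per 4-minute set, so 16 per session and 192 over 12 sessions: 192 x 2.29 = 440 m. At an illustrative Vt of 15 km/h, D is 68.75 m and the programme total is 192 x 68.75 = 13,200 m, so 440 m is about 3%.

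**The case against.** The strongest reply is that the plan never says when players learn their arm. Players cannot be blinded to a training programme, so the non-blinded label may mean only that, and the arm might in practice be announced at session 1. Figure 1 is not visible and may show more. This stands in part: a reader might infer that players are told their arm before baseline, and the text does not establish it. But the text does put allocation first, and it contains no statement that withholds the arm.

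The plan also has protections. The allocating researcher does not test and testers are uninformed, which limits tester-driven bias. Heart rate and RPE are recorded through the Yo-Yo IR1, the Wingate uses standardized encouragement, and the first repeated sprint is checked against the player's own 40 m sprint with a 3% margin. These could help to spot poor effort. None removes the problem; the 3% check, for instance, would miss a player who holds back in both sprints.

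The size is hypothetical. No document supports a shift of 0.1, 0.2 or 0.3 SD, and at 0.1 SD with r = 0.5 the inflation is under one percentage point. The incentive in the dribbling arm also presumes that players know how their distance is set. All of this stands.

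Three stronger readings are tempting and should not be drawn:

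- That no analysis could help. ANCOVA reduces the bias, and a post-test-only comparison avoids it.
- That every pre-post measure is affected. Anthropometric measures hardly depend on effort, and the enjoyment scales are collected after training, not pre and post.
- That allocation may precede consent. Section 3.1 says "Before data collection, the written informed consent should also be provided" and has the procedures explained at the screening-baseline stage. The timing of consent relative to allocation is unstated, not shown to be wrong.

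**Conclusion.** The point holds for the effort-based performance outcomes: Yo-Yo IR1 and the VO2max derived from it, Wingate, sprints and repeated sprints. The written order lets baseline effort depend on the arm, the stated safeguards do not reach the players, and the planned group x time test passes any such shift through in full.

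The order of steps and the missing statement about players and coaches are facts of the text. The shift sizes, the correlations and the premise of no true difference are assumptions. Under them, the false-positive rate is 5.7-11.3% at r = 0.5 and 6.7-22.0% at r = 0.8, against a nominal 5%. Whether any bias would occur, and in which direction, cannot be known from the documents. The case for acting is that prevention is almost free before the first allocation, whereas afterwards only partial or less powerful analytic remedies remain.

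**What to change.** In section 3.2 and the flowchart, reverse the two steps: consent, eligibility check, and all baseline tests completed and recorded; then allocate all players in one batch before session 1. The terminal speed for the dribbling arm is already available by then.

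If the order must stay, add one sentence stating that the arm is withheld from players and coaches until every baseline test is complete, and say who holds the list.

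The cost is a reordered paragraph and flowchart. Table 1 places baseline in weeks 1 and 2 and training from week 3, so the batch allocation fits between them without delay, and the sample size of 42 is unaffected. Changing the analysis to ANCOVA would not substitute for this.
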